4.7 Missed visit/lost-to-follow-up

Site research staff will make every effort to have participants complete follow-up study visits. Should the participant be willing, site staff will conduct the appropriate visit off-site (not in the clinic) at locations which assure adequate privacy and confidentiality. If a participant refuses any protocol-specified procedures, this should be appropriately documented in the clinic/chart notes.

For visits that are designated as in-person, per the Study Schedule of Visits and Procedures, inperson contact with participants is the preferred method of collecting study data. However, there may be rare circumstances in which telephone contact may be the only method available for collecting data. Determining that a telephone visit is necessary will be done only after all other options for scheduling the visit have been explored (e.g., earlier or later office hours, interim visits, off-site visits). All scheduling efforts will be documented in the participant's chart notes and/or contact logs.

4.8 General Procedures

Study visits may take place at a location identified by study staff which assures adequate privacy and confidentiality, such as, the venue, the study clinical site, mobile vans, or another public area.

Semi-structured interviews and FGs will be conducted by trained staff. When possible interviewers and FG moderators will be ethnically matched to participants. All interviews and FGs will be recorded and transcribed by qualified personnel. Personal identifiers will be removed from final transcripts. Focus group participants will not be asked to identify themselves within the group, but will instead be encouraged to provide a "made-up" name. Further details regarding the conduct of interviews and FGs can be found in the SSP.

Selection of items for inclusion in the behavioral survey is guided by prior research experience using measures that have shown satisfactory reliability in assessing HIV-risk factors and prevention practices among ethnic minority women and may include, but is not limited to, the following domains:

- Sociodemographic data required of US National Institutes of Health (NIH) studies and needed to describe the characteristics of the participants and their sex partners, including age, living situation, income, race and ethnicity, education, and length of sexual relationships. More constant variables such as race, age and education will be collected at baseline only.
- Sexual behavior, including frequency of vaginal and anal intercourse, condom use characterized as the proportion of condom protected vaginal and anal acts of intercourse over time (e.g., the past 90 days and 6 months) and condom use at last intercourse, number of sex partners, concurrency of sexual partners, partners' risk status (e.g. concurrency, substance use, incarceration history) and transactional sex (e.g. exchange of sex for drugs, money, or shelter). Sexual behaviors will be assessed with a primary partner (defined as the man with whom the respondent has the committed long-term relationship) and other partners.
- Adaptations of commonly used instruments to assess various risk factors, including exposure to domestic violence, depression, alcohol dependence, and substance use.
- Social harms.
- Participant interest in HIV prevention studies, such as group interventions (e.g., Project SAFE), individual interventions (e.g., microenterprise, vaccines) and community level interventions.

Interviewers will be trained in recall-enhancing techniques, such as using calendars and visual clues to enhance accurate reporting of sexual and other sensitive behaviors.

HIV pre-test and risk reduction counseling will be provided according to each site's state standards, at minimum.

5 STUDY PROCEDURES FOR MALE PARTICPANTS

Screening

Prescreening activities with men will take place at venues identified by sites conducting ISIS. The purpose of the prescreening activities is to provide general information about the study to potential participants and to assess interest in screening for the study. No identifiable study data will be recorded until after written informed consent has been obtained. Participants who appear eligible and are interested in the study will be invited to consent for screening and enrollment in the study. For participants who do not meet the study eligibility criteria, the prescreening and/or screening process may be discontinued when ineligibility is determined. Men who participate in the focus group will be considered enrolled. Study procedures for male participants will follow the applicable general procedures outlined in Section 4.8.

Administrative, Behavioral, And Regulatory Procedures

- Obtain verbal informed consent for screening or written consent for screening and enrollment.*
- Collect locator information, if written consent obtained.**
- Administer eligibility screener.
- Collect demographic information.
- Schedule (or conduct) FG, if eligible.

*See Section 8.2 and the SSP for details on screening and enrollment informed consent procedures. **Note: No identifiable data will be collected prior to obtaining written informed consent. If the participant has provided verbal informed consent for screening and appears eligible, obtain written informed consent for enrollment prior to collecting identifiable information.

Enrollment Visit

Administrative, Behavioral, And Regulatory Procedures

- Obtain informed consent for enrollment (if not obtained at screening).*
- Collect/update locator information.
- Confirm eligibility
- Administer behavioral questionnaire.
- Conduct FG.
- Offer condoms

*See Section 8.2 and the SSP for details on screening and enrollment informed consent procedures.

There are no laboratory or clinical/counseling procedures for male qualitative component participants.

6 SAFETY MONITORING AND ADVERSE EVENT REPORTING

6.1 Safety Monitoring

As ISIS is an observational cohort study, standard adverse event (AE) reporting will not be undertaken. The study team will monitor for and track serious adverse events (SAEs) related or possibly related to study procedures and/or to participation in the study. Such events that are unanticipated will be reported to the Division of AIDS (DAIDS) HPTN Program Officer at the same time as they are reported to IRB/ECs according to pre-established written procedures, as required by 45 CFR 46. This information will not be recorded on CRFs or entered into the study database. Data on social harms will be collected at each in person follow-up visit as part of the overall assessment of participant safety.

7 STATISTICAL CONSIDERATIONS

7.1 Review Of Study Design

The primary objective of this study is to estimate the overall HIV-1 incidence rate among 2,000 women in the US from defined geographic areas with high HIV prevalence and poverty. We will not attempt to precisely characterize HIV incidence rates within each community; rather, we will show that the proposed strategy for identifying women and communities will provide a precise estimate of HIV seroincidence across all ten communities.

This study will enroll 2,000 women at risk of HIV acquisition across 10 communities, including approximately 1,900 seronegative women and approximately 100 HIV seropositive women who have no reported history of past HIV diagnosis. Women who have a reactive HIV rapid test result will have samples sent to the HPTN NL for testing that includes the BED assay. Results from these tests will be combined with clinical data. to identify participants with recent HIV infection. Clinical data will likely include, but will not be limited to, the following: current/previous antiretroviral therapy, CD4 counts, etc. The multi-assay algorithm to define recent HIV infection based on cross-sectional testing will be defined and validated before it is used to generate HIV incidence estimates in ISIS. Participants will be followed for up to 12 months, with repeated collection of samples for HIV testing at 6 and 12 months. The 6- and 12-month HIV testing results will be used as follows:

Among those who are seronegative at study entry:

- To identify cases of incident HIV infection (traditional seroconversion analysis).
- To validate the "sensitivity" of the algorithm used for cross-sectional incidence testing.

Among those who are seropositive at study entry:

• To validate the "specificity" of the algorithm used for cross-sectional incidence testing.

7.2 Accrual, Follow-Up, and Sample Size

For this study, the ISIS team will identify 10 communities from which women at risk of HIV acquisition will be recruited using criteria outlined in Section 3.1. Within each community, 200 women will be enrolled. Women enrolled in the first 3 months at each site will be followed for 12 months, while women enrolled in the next 3 months at each site (months 4 - 6) will be followed for 6 months. However, if accrual is slower than anticipated (i.e., if < 50% of the cohort is enrolled by month 3), we will extend the follow-up duration to 12 months for individuals enrolled in month 4

and, if needed, in month 5. We assume that approximately 5% of the enrolled cohort will be HIV seropositive at study entry. The HIV seronegative women will be followed for seroconversion; the HIV seropositive women will be followed to help determine whether they had recent versus non-recent HIV infection at enrollment, using a multi-assay laboratory algorithm for determination of HIV incidence. This will provide a total effective follow-up period for incidence calculations of ~220 person-years per community (about 40% from the enrollment visit based on a retrospective window period of 160 days, and 60% from the prospective longitudinal follow-up). A maximum of 10% loss-to-follow-up per year is assumed, yielding a total of ~210 person-years per community for analysis. Note that the estimated window period of 160 days is based on the BED assay, which is likely to be a major component of the multi-assay HIV incidence algorithm.

Based on a recent infection window period of approximately 160 days, with a seropositivity rate of 5% and a seroincidence rate of 2%, the number of recently infected participants at enrollment is expected to be approximately 16. Assuming a similar seroincidence rate over the prospective follow-up period, and accounting for loss to follow-up, an additional 26 infections should be observed after enrollment (18 infections in months 1-6; 8 infections in months 7-12). Overall, this should yield approximately 42 incident infections. Assuming that a multi-assay algorithm for identifying recent infections is developed and validated at the HPTN NL in the near future, it will be possible to combine the cross-sectional HIV incidence estimate from enrollment with the longitudinal incidence estimate from follow-up into a single incidence estimate. Table 3 (below) gives the width of a 95% CI for the HIV incidence rate (pooling across communities) as a function of the total number of person-years in the feasibility study, assuming an underlying incidence of 2% per year and coefficient of variation (CV) in incidence across communities of 0.0 (we will, however, use the data from this study to estimate the CV – see Section 7.3.2). Once the multi-assay algorithm for identifying recent infections is validated, then the combined cross-sectional and longitudinal data will provide 2,000 – 2,200 person-years for incidence estimation and a 95% confidence interval (CI) of ± 0.0066 or less. An incidence estimate based only on the longitudinal (follow-up) data will include 1,200 – 1,300 person-years.

Person-years	800	1200	1600	2000	2400
CV = 0	± 0.010	0.0085	0.0074	0.0066	0.0060
CV = 0.1	± 0.010	0.0087	0.0075	0.0067	0.0061
CV = 0.2	± 0.011	0.0091	0.0080	0.0071	0.0065

 Table 3. Width of 95% CI for HIV-incidence based on total person-years of data, pooled across all communities

7.3 Data Analysis

The primary analysis shown below describes how HIV incidence will be estimated, both separately from the cross-sectional and longitudinal components of the study, and using both sources of data combined into an overall incidence estimate.

Secondary analyses describe how we will summarize the cohort of women, compare the crosssectional and longitudinal incidence estimates, and estimate the community-to-community variation in HIV incidence. We also describe statistical methods to be used in validating the laboratory algorithm for identifying recent infections.

7.3.1 Primary Analyses

Data from all communities will be pooled to estimate HIV incidence. Below, we describe approaches for estimating incidence from either the cross-sectional portion of the study, or the longitudinal portion of the study. If a validated algorithm for identifying recent infections is developed (which we believe is likely) then these two estimates will be combined into a single incidence estimate. If a validated algorithm for identifying recent infections cannot be developed, then only the incidence estimate based on longitudinal follow-up will be reported.

An estimate of HIV incidence based on identification of recent infections at study entry (retrospective estimate) is given by the formula (31)

$$I_r = \frac{F_1 N_i}{N_{sn} + F_1 N_i}$$

where N_i is the number of recently infected individuals, N_{sn} is the number of HIV negative individuals in the sample and F_1 is a scaling factor to account for the window size (W) i.e. $F_1 = 365/W$. For example, for the BED assay, Parekh et al. (33) uses the value W = 160 days. The variance of this incidence estimate is

$$Var(I_r) \approx \frac{F_1 I_r}{N_{sn} + F_1 N_i}$$

Bootstrap procedures may also be used to evaluate the uncertainty in the estimated incidence. As noted above, an incidence estimate based on the cross-sectional component of the study will only be generated if a validated approach for identifying recent infections is developed. Complete details on the laboratory algorithm and methods to be used for estimating HIV incidence estimate will be developed jointly by the NL and SDMC, and will be described in detail in the Statistical Analysis Plan prior to the final analyses of the data from this study.

Incidence will be estimated from the follow-up data by the standard formula

$$I_{f} = \frac{N_{f}}{Y_{f}}$$

where N_f is the number of incident infections observed over follow-up and Y_f is the total person years of follow-up (expected to be 1,200 – 1,300 person-years). The variance of this estimate is

$$\operatorname{Var}(I_{f}) = \frac{I_{f}}{Y_{f}}.$$

The two incidence estimates can be pooled using a weighted average

$$I_p = v * I_r + (1 - v) * I_f$$

where the weighting factor is $v = Var^{-1}(I_r)/(Var^{-1}(I_r) + Var^{-1}(I_f))$. The variance of this estimator is $1/(Var^{-1}(I_r) + Var^{-1}(I_f))$ and can be used to compute CIs for I_p .

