The assays described above, including the BED assay, were developed and optimized for subtype B HIV-1. Though there are limited published studies on BED use in North American patients, performance of the BED assay in estimating HIV incidence was evaluated in the AIDSVAX B/B (28) vaccine trial, a trial conducted in North America and Europe. The BED assay was performed every 6 months on specimens obtained from the 3-year longitudinal cohort. There was excellent agreement between the observed and BED-estimated incidence for all intervals with cumulative annualized incidence observed in the cohort of 3.10 per 100 person-years (95% CI 2.57-3.63) compared with the corresponding BED-estimated incidence of 2.91 (2.30-3.53).(28) In a second study, Priddy et al (34) reported excellent agreement between Vironostika-LS and BED in samples procured in Atlanta, Georgia. However, in the international setting, substantial errors in incidence estimates have been seen when BED has been used to analyze non-B HIV-1. BED has overestimated incidence rates by 2-3 fold (20) and by as much as 6-fold (36) in some international settings with high prevalence rates. These overestimates have led to recent recommendations (2) against the use of BED for "routine surveillance applications, neither for absolute incidence estimates, nor for monitoring trends." Because ISIS will be performed in the US, where the majority of women are likely to have subtype B HIV infection, subtype-related performance problems should be minimal. In ISIS, results obtained with the BED assay will be analyzed in the context of clinical information and data obtained from other laboratory assessments (e.g. CD4 cell count, avidity testing), thereby improving accuracy of BED-based incidence estimates. In addition, use of a cohort design allows ISIS to validate BED results obtained from study participants at enrollment by repeating BED testing at subsequent follow-up visits. This approach of combining use of BED with other assays, clinical information, and longitudinal assessments should maximize the accuracy of incidence estimates in ISIS. Furthermore, the data obtained will be invaluable for validating and optimizing laboratory algorithms for HIV incidence determination. This information

will be essential for the design of any subsequent prevention trial in US women, and for the design of future cross-sectional HIV trials utilizing an HIV incidence endpoint.

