These data, as well as data from other HPTN and non-HPTN studies, will be used by the NL to optimize and validate an algorithm for identifying recent infections among HIV seropositive individuals. It is likely that the BED assay (31), other laboratory assays, and clinical data will be used in such an algorithm. We define the "sensitivity" of the algorithm as the probability that the algorithm defines an individual as recently infected (within some predefined window period, W) given that he or she is in fact recently infected. The "specificity" is the probability that an individual who is not recently infected is classified as not recent. Women who seroconvert during the longitudinal follow-up portion of this study will be used to validate the sensitivity of the algorithm (i.e. a high proportion of samples from women who seroconvert during the study should be classified as recently infected). Women who are seropositive at entry and contribute 6- and/or 12-month samples in the longitudinal follow-up will be used to validate the specificity of the algorithm (i.e. the samples collected at 6 and 12 months should be classified as not recent). Sensitivity and specificity will be estimated by simple proportions and exact methods will be used to generate CIs.

Finally, these data will be used to test the hypothesis

Ho:
$$I_r = I_f$$

Ha: $I_r \neq I_f$.

Effectively, this is testing whether or not the incidence observed in cross-sectional testing at study entry is similar to the incidence observed over follow-up. Assuming 42 total incident infections and 40% of the person-years from the cross-sectional incidence estimate versus 60% of the person-years from the longitudinal incidence estimate, we will have 80% power to detect a relative incidence (I_r / I_f) of 2.4.

Another important secondary analysis of these data will be to estimate the CV of incidence among the communities. The estimated CV is given by

$$CV = \frac{\sqrt{S^2 - I_p * \sum_j \left(\frac{M}{Y_j}\right)}}{I_p}$$

where S^2 is the observed variance in incidence across the M=10 communities and Y_j is the number of person-years from community j.(17) This information will be important in determining sample size for future intervention trials. Hughes(18) describes how baseline data such as these can be used to help inform the design of such trials.

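### The stated cross-sectional incidence estimator has no correction for false-recent results, and its variance carries no uncertainty in the false-recent rate or the window, although Section 7.3.2 measures the algorithm's sensitivity and specificity

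*Protocol*

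**What the plan says.** Section 7.3.1 of the protocol sets I_r = F1·N_i/(N_sn + F1·N_i), "where N_i is the number of recently infected individuals, N_{sn} is the number of HIV negative individuals in the sample", with F1 = 365/W. For the BED assay it cites a source that "uses the value W = 160 days". The variance is F1·I_r/(N_sn + F1·N_i), and a bootstrap is optional. I_r is then pooled with the follow-up estimate I_f by inverse-variance weights to give I_p.

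Section 7.3.2 defines sensitivity and specificity relative to a predefined window. Seroconverters in follow-up inform sensitivity. The 6- and 12-month samples of women seropositive at entry "will be used to validate the specificity of the algorithm". No step returns either quantity to I_r, Var(I_r) or I_p.

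The planning figures are "approximately 1,900 seronegative women and approximately 100 HIV seropositive women who have no reported history of past HIV diagnosis" (Section 7.1). Section 7.2 assumes 2% incidence, and "the number of recently infected participants at enrollment is expected to be approximately 16"; in follow-up, "an additional 26 infections should be observed after enrollment".

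Section 1.2.3 acknowledges that several factors can make an infection look recent when it is not, and reports that "BED has overestimated incidence rates by 2-3 fold (20) and by as much as 6-fold (36) in some international settings".

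Three provisions limit the exposure. I_r is produced only if a validated algorithm exists (Sections 7.1 and 7.3.1). BED is combined with CD4 count, avidity and clinical data (Section 1.2.3). Full details of the algorithm and the estimation methods are left to the SAP (Sections 7.3.1 and 9.5).

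**The concern.** The formula treats the number classified as recent as if it were the number recently infected. Long-standing infections are expected to outnumber recent ones by about five to one, and each false recent is multiplied by F1 = 2.28. Even a fairly specific algorithm can therefore shift I_r. The variance treats the false-recent rate as zero and W as known, so the interval is too narrow as well as possibly off-centre.

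The relative bias grows as true incidence falls, because the recent count shrinks while the pool of long-standing infections does not. Section 1.2.4 says the findings will be used to judge whether incidence is high enough to power a trial with an incidence endpoint, so the direction and size of this error should not be left to chance.

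**Working it through.** **Inputs.** N_sn = 1,900 and N_pos = 100 (Section 7.1). W = 160 days, so F1 = 365/160 = 2.281. Incidence is 2% (Section 7.2). Y_f = 1,250, the midpoint of the 1,200–1,300 person-years in Section 7.3.1. The false-recent rate, FRR = 1 − specificity, is assumed at 2%, 5% and 10%, because the protocol gives none.

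**The plan's own figures.** Recent infections at entry: 0.02 × 1,900 × 160/365 = 16.7. Inverting the I_r formula gives 17.0. Both agree with the stated 16 or so, and both assume no false recents. With 17.0 recent, about 83 are long-standing.

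**Effect on I_r and I_p.** The expected count is N_i = sens × 17.0 + FRR × 83.0. I_f is held at 0.0200, so Var(I_f) = 0.02/1,250 = 1.60 × 10⁻⁵.

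Example, FRR 5% and sensitivity 1:
- N_i = 17.0 + 4.15 = 21.15
- I_r = 48.25/1,948.25 = 0.0248
- Var(I_r) = 2.281 × 0.0248/1,948.25 = 2.90 × 10⁻⁵
- v = 0.356, down from 0.405 with no false recents
- I_p = 0.356 × 0.0248 + 0.644 × 0.0200 = 0.0217

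| True incidence | Sens | FRR | N_i | I_r | I_p |
|---|---|---|---|---|---|
| 2% | 1.0 | 2% | 18.66 | 2.19% (+10%) | 2.07% (+4%) |
| 2% | 1.0 | 5% | 21.15 | 2.48% (+24%) | 2.17% (+8.5%) |
| 2% | 1.0 | 10% | 25.30 | 2.95% (+47%) | 2.30% (+15%) |
| 2% | 0.9 | 2% | 16.96 | 2.00% (none) | 2.00% (none) |
| 2% | 0.9 | 5% | 19.45 | 2.28% (+14%) | 2.11% (+5%) |
| 2% | 0.9 | 10% | 23.60 | 2.76% (+38%) | 2.25% (+12.5%) |
| 1% | 1.0 | 5% | 12.99 | 1.54% (+54%) | 1.16% (+16%) |

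The 1% row has 8.4 true recents and keeps 100 seropositive women. With Y_f at 1,200 or 1,300, the I_p inflation at FRR 5% and 2% incidence is 8.7% or 8.3%. Net inflation at 2% incidence requires FRR above about (17/83) × (1 − sens), or roughly 0.2 × (1 − sens).

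**Would the planned comparison of I_r with I_f reveal it?** Assume two-sided α = 0.05 (the protocol states none), 42 events and a 40/60 split. Power = Φ(√(42 × 0.4 × 0.6) × ln(ratio) − 1.96). At ratio 2.4 this gives 0.79, reproducing the stated 80%. At 1.5 it gives 0.25 and at 1.25 it gives 0.11.

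**How well could the false-recent rate be known?** If 84 women (100 − 16) were tested and none was falsely recent, the exact 95% upper limit would be 1 − 0.025^(1/84) = 4.3%.

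**Precision after correction.** N_adj = (N_i − (1 − spec) × N_pos)/(sens + spec − 1). Treat N_i as Poisson, estimate specificity on 84 women and use the delta method, dI_r/dN = F1·N_sn/(N_sn + F1·N)² = 0.001153.
- No misclassification: SE(N) = √17.0 = 4.12; pooled half-width 0.0060.
- Spec 0.95, sens 1 taken as known: N_adj = (21.15 − 5)/0.95 = 17.0; SE = √(21.15/0.95² + (83/0.95 × 0.0238)²) = 5.27; half-width 0.0065.
- Spec 0.95, sens 0.90 estimated on 26 seroconverters: N_adj = (19.45 − 5)/0.85 = 17.0; SE = 5.81; half-width 0.0067.

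Uncertainty in W is not yet included.

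**The case against.** **Deferral to the SAP.** The SAP is to describe the estimation methods as well as the laboratory algorithm, and the algorithm did not exist when the protocol was written. A correction may therefore be in the SAP. That stands, and it lowers the severity. It does not remove the point, because the only estimator and variance that the protocol states are uncorrected.

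**Validation requirement.** A reader might infer that raw BED counts go straight into the primary estimate. The protocol does not support that: it requires a multi-assay algorithm validated before use, and reports I_f alone otherwise. What remains is that no performance threshold is stated, and a validated algorithm can still have a false-recent rate that matters here.

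**Relevance of the overestimation.** The 2- to 6-fold figures come from international settings and, as Section 1.2.3 presents them, non-B infection. The same section reports 2.91 by BED against 3.10 observed per 100 person-years in a trial conducted in North America and Europe, without saying whether the BED figure was corrected. The large multiples should not be carried over to this study.

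**Size in the primary estimate.** A reader might take the I_r percentages as the bias in the primary result. Pooling dilutes them: at FRR 5% and 2% incidence, I_p moves by 0.0017, against a stated half-width of 0.0066. Imperfect sensitivity can offset a small false-recent rate entirely. Both points stand.

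**Risk in the obvious remedy.** Women found positive at entry are referred to care (Section 2.3.1), so some may be on antiretrovirals by months 6 and 12, and Section 1.2.3 names such treatment as a cause of misclassification. Specificity from those samples may be lower than at enrollment, and using it unadjusted could over-correct. This stands and shapes the fix.

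**Conclusion.** The point holds as a weakness in the stated estimator and should be fixed; it is not a must-fix. With an imperfect algorithm, the formula in Section 7.3.1 generally gives a biased I_r, and its interval omits uncertainty in the false-recent rate and W. At 2% incidence and perfect sensitivity, assumed false-recent rates of 2–10% raise I_r by about 10–47% and I_p by about 4–15%. At 1% incidence, a 5% rate raises them by about 54% and 16%. At sensitivity 0.90 a 2% rate cancels, so the sign of the error is not fixed. The planned test of I_r against I_f has too little power at these ratios to act as a safeguard.

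A reader might also infer that a low-incidence cohort would be mistaken for one able to support an incidence-endpoint trial. The documents do not show that: in the 1% case I_p is 1.16%, and I_f is estimated separately.

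These sizes rest on the assumed false-recent rates, 100 seropositive women at entry, W = 160 days and 1,250 follow-up person-years.

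**What to change.** State in Section 7.3.1, and carry into the SAP, that I_r uses a count corrected for false recents.

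- If W is a fixed cut-off with sensitivity and specificity defined against it, as in Section 7.3.2, use N_adj = (N_i − (1 − spec) × N_pos)/(sens + spec − 1), with N_pos the number seropositive at entry.
- If W is a mean time classified as recent, correct only for the long-term false-recent rate. Dividing by sensitivity as well would correct twice.
- Take specificity from samples comparable to enrollment: external validation panels, or follow-up samples excluding women who have started antiretrovirals.
- Carry the uncertainty in specificity, sensitivity and W into Var(I_r) and the pooling weight, by delta method or bootstrap.
- Say what performance counts as validated.
- Report the uncorrected I_r and I_f beside the corrected and pooled estimates.

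The cost is wording, some programming and a wider interval; no new visits or samples from participants are needed. At specificity 0.95 the pooled half-width goes from about 0.0060 to about 0.0065–0.0067 before uncertainty in W, so the ±0.0066 in Section 7.2 may need restating.

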It is expected that approximately 1,900 women will be HIV seronegative at study entry, and approximately 100 women will be HIV seropositive without past history (at study entry) of HIV diagnosis. Laboratory results from the enrollment, 6- and 12-month samples of each seropositive woman will be evaluated using current best algorithms for determination of recent HIV incidence. Participants who have BED and other laboratory results consistent with recent HIV infection will be considered "incident by BED". Participants with HIV seroconversion during follow-up (i.e. who have a negative or indeterminate WB, with a positive WB 6 or 12 months later) will also be classified as having recent HIV infection ("incident by follow-up"). The HIV status of other participants will be assessed, based on the results of WB testing, CD4 cell count, BED, and other assays. Samples collected at each study visit will be stored for future testing (See Section 9).

All women with confirmed HIV infection will be rapidly referred for HIV care, treatment and support. Study CRSs will be encouraged to have memoranda of agreement with multiple organizations rendering care and services, so that women will be able to choose from multiple care and treatment organizations and will not be limited to receiving care from the home institution of the CRS. Should a participant desire care outside of their community, every effort will be made to assure connection to quality care.

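### The printed pooling rule for the primary incidence estimate is a harmonic mean that favours the lower component: nearly harmless at the planned 2%, material at about 1% or below or when the components diverge

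*Protocol*

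**What the plan says.** Section 7.3.1 gives two incidence estimates. The cross-sectional one is I_r = F1·N_i/(N_sn + F1·N_i), with F1 = 365/W and approximate variance F1·I_r/(N_sn + F1·N_i). The longitudinal one is I_f = N_f/Y_f, with variance I_f/Y_f. If a recency algorithm is validated, which the section expects, "then these two estimates will be combined into a single incidence estimate".

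The only combination rule given is this: "The two incidence estimates can be pooled using a weighted average". The weight v on I_r is its inverse variance divided by the sum of the two inverse variances. The reciprocal of that sum is the variance of the pooled estimate I_p "and can be used to compute CIs for I_p".

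Pooling depends on validation of the algorithm. It does not depend on the test of I_r = I_f in Section 7.3.2. Nothing is said about a component with no events, or about the weights being functions of the estimates.

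**The concern.** Inverse-variance weighting is optimal when the variances are known or nearly independent of the estimates. Here each variance is a Poisson-type variance evaluated at its own point estimate. A component that falls low by chance also looks more precise and is given more weight. The resulting error runs in one direction, downward, and it grows as the event counts shrink.

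I_p answers the primary objective. It also enters the formula for the coefficient of variation in Section 7.3.2, and it informs whether incidence is high enough to power a later trial (Section 1.2.4). A systematic understatement, with intervals that miss mostly on the low side, carries into those decisions.

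**Working it through.** **Inputs**
- Section 2.3.1: "It is expected that approximately 1,900 women will be HIV seronegative at study entry", so N_sn = 1,900.
- Section 7.2, for W = 160 days and the planning rate: "Based on a recent infection window period of approximately 160 days, with a seropositivity rate of 5% and a seroincidence rate of 2" per cent. F1 = 365/160 = 2.281.
- Section 7.2: 16 recent infections expected at enrollment and 26 in follow-up, 42 in all; loss to follow-up 10% per year.
- Sections 7.2 and 7.3.1: Y_f = 1,200-1,300 person-years. I use 1,300; results at 1,200 are similar.
- My assumptions: independent Poisson counts, and a Wald interval I_p ± 1.96·SE from the stated variance (the protocol does not name the interval).

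**The plan's own counts**
- Enrollment: 1,900 × (160/365) × 0.02 = 16.7 (plan: 16).
- Follow-up, with half the women followed for 12 months: 0.02 × 1,900 × 0.5 × 0.95 = 18.05, plus 0.02 × 950 × 0.5 × 0.90 = 8.55, total 26.6 (plan: 26).
- Sum 43.3 against 42, so the planning figures are reproduced to within about one event.

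**Algebra**
1. Let Y_r = N_sn/F1 + N_i. Then I_r = N_i/Y_r and Var(I_r) = I_r/Y_r, the same form as Var(I_f) = I_f/Y_f.
2. The inverse variances are Y_r/I_r and Y_f/I_f.
3. Hence I_p = (Y_r + Y_f)/(Y_r/I_r + Y_f/I_f), a person-year-weighted harmonic mean. It can never exceed the corresponding arithmetic mean, (N_i + N_f)/(Y_r + Y_f).

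**Worked splits of 42 infections, Y_f = 1,300**
- 16 recent, 26 follow-up: Y_r = 832.9 + 16 = 848.9; I_r = 1.885%; I_f = 2.000%; I_p = 1.953%. Like-for-like comparator: 42/2,148.9 = 1.955%.
- 26 recent, 16 follow-up: Y_r = 858.9; I_r = 3.03%; I_f = 1.23%. The weight on I_r is 0.21, whereas its share of person-time is 858.9/2,158.9 = 0.40. I_p = 1.61%, against 42/2,158.9 = 1.95%.
- 8 recent, 34 follow-up: I_p = 1.55%, against 1.96%.

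The pull is downward whichever component is the higher one.

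**Repeated-sampling behaviour under a common rate (exact enumeration, Y_f = 1,300)**

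| True incidence | Bias of I_p | 95% Wald coverage | Chance of a zero component |
|---|---|---|---|
| 2% | -2.3% (-3.1%) | 92.9% (92.4%) | about 4 in 10^8 |
| 1% | -4.7% (-5.1%) | 89.5% (89.2%) | 0.02% |
| 0.5% | -9.7% (-9.9%) | 85.5% (85.3%) | 1.7% |
| 0.31% | -16% | 81% | 9% |

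Figures outside parentheses take the true I_r on its own proportion scale and so isolate the weighting. Figures in parentheses generate N_i from a rate, which adds the small effect of I_r being a proportion while I_f is a rate. At 2% the bias is about one event (0.023 × 43 ≈ 1), and 6-7% of intervals lie wholly below the truth against a nominal 2.5%. Samples with a zero component are counted as I_p = 0. In the samples with events in both components, the bias at 0.5% is about -8%.

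**Zero events.** If N_i = 0 or N_f = 0, the estimated variance is 0 and its inverse does not exist. In the limit I_p = 0 with SE = 0, even when the other component has infections.

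**The case against.** The strongest reply is that the design rate is 2% and little goes wrong there. The bias is about 0.0005 against a standard error of about 0.003, coverage is about two points low, and a zero component is practically impossible. At 16 and 26 infections the printed variance gives ±0.0059, inside the ±0.0066 of Section 7.2. All of this stands, and it limits the severity.

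The wording is also permissive: the estimates can be pooled, bootstrap methods may be used, and full details are left to the statistical analysis plan, which is not shown. This stands only in part. The printed rule is the only one given for the primary estimate, and bootstrapping I_p would not remove its bias.

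Three stronger readings are tempting but not supported.
- A reader might infer that the 1.61% against 1.95% example measures bias. It does not. If the two incidences truly differ, there is no common rate to be biased against, and the question becomes whether to pool at all. The example shows how far the weights can move, and a ratio of 2.46 would be unusual under a common rate.
- A reader might infer a substantial chance of a zero estimate from the 0.16 cited in Section 1.2.1, which would give about 36%. That rate carries no units and comes from women tested in public settings, whereas this study deliberately seeks women at higher risk. Strictly, the formula is then undefined; it does not return zero.
- A reader might take the statement in Section 7.3.2 that "we will have 80% power to detect a relative incidence" of 2.4 as evidence of a pooling defect. It is a power statement for a separate test and shows none.

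**Conclusion.** The point holds and should be fixed. As printed, the pooled primary estimate is a harmonic mean with a one-directional downward bias and intervals that under-cover. With N_sn = 1,900, W = 160 days, Y_f = 1,300, Poisson counts and a Wald interval, the harm is small at 2%, where the bias of -2.3% comes from the weighting (about -3.1% with the proportion/rate mismatch). It becomes material at about 1% incidence or below, or when the two components diverge. The undefined zero-event case is negligible at 2%, about 1.7% at 0.5% and about 9% at 0.31%. The documents do not support calling the estimate unusable at the planned values.

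**What to change.** Replace the inverse-estimated-variance weights in Section 7.3.1, and in the statistical analysis plan, with one person-time-weighted estimator:

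I_p = (N_i + N_f)/(N_sn × W/365 + Y_f), with an exact or mid-P Poisson 95% interval.

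Under a common rate this was unbiased in the same enumeration when N_i was generated from that rate, with exact-interval coverage of about 96-98%. It stays defined when one component has no events. It also removes the mismatch between a proportion and a rate.

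Do not describe it as identical to setting v = Y_r/(Y_r + Y_f). That version keeps N_i in the denominator and differs by about 1%: with 26 recent and 16 follow-up infections the two give 42/2,132.9 = 1.969% and 42/2,158.9 = 1.945%.

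The cost is one line of text, with no new data and no change in sample size. The interval is slightly wider. For 42 infections the exact limits are 1.42% to 2.66%, a half-width of about 0.0062 against 0.0059 now, still within the ±0.0066 of Section 7.2.
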